3.0 STUDY ENROLLMENT AND PARTICIPANT ELIGIBILITY

3.1 Study Enrollment

Location

Health beneficiaries of UHH newly diagnosed cancer or relapsed or recurrent cancer may be referred by oncology provider clinics who partner with UHH.

Enrollment Procedures

UHH Staff assigned to the program will target potential patients on an ongoing basis using their claims data system. This includes data from a variety of sources including but not limited to Daily Inpatient Reports; referrals from hospital staff, PCPs and Specialists; referrals from other UHH staff such as those working in customer service; and referrals from Union staff and participants. The study staff will review all potential patients with newly diagnosed or recurrent disease no matter the stage or type to determine eligibility for the program. After the site PI and

study staff conduct proper screening (see below section titled “Screening Procedures” for specific details), the program will be explained to patients and patients will then be enrolled in the study.

Screening Procedures

The Site PI and staff will utilize the following claims data system documents and procedures to also screen for patients who fit the inclusion criteria listed in 3.2. Screen failures will not be included in the study data. The PI will keep a record of history and reasons for screen failures; however, any patient information gathered during this process will be destroyed.

Consent Procedures

The study staff will discuss the intervention with the patient, at the first point of contact, after eligibility has been confirmed. The study staff will introduce the program and describe the program aims and objectives. Patients will be provided adequate time to make an informed decision regarding their participation. Patients who refuse participation or have no capacity for decision-making or consent will not be included in the study.

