3.2 Participant Criteria

Inclusion criteria

1. Newly diagnosed patients with a cancer diagnosis.
2. Patients with any relapse or progressive disease (any cancer diagnosis) as identified by imaging or biopsy and confirmed by physician.
3. The patients must be 18 years or older.
4. Patients must have the ability to verbally consent and understand study procedures.

Exclusion Criteria

1. Inability to consent to the study.
2. Patients without a newly diagnosed malignancy or patients without relapse of disease.
3. Patients not eligible for fund benefits.

Criteria for Removal from Study

Any patients or families of patients in the intervention arm who withdraw consent will be removed from the study. Upon removal, usual care will be restored for these patients.

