The FACT-G is a quick, validated, 27- item compilation to assess QOL domains with discriminate ability and sensitive to changes in QOL over time.

The Satisfaction with Decision scale is a quick, validated 6-question survey to assess patient experiences with decision-making.

The Patient Activation Measure is a validated measure used to assess patient activation.

[name] has used these measures with success in a similar project completed at the Palo Alto Veterans Hospital (Palo Alto, CA). Unite Here Health uses Patient Activation Measure as part of usual care at their organization.

If patients feel discomfort while conducting their surveys, they may choose to not complete them. If there are any psychological events that occur during the study, these will be reported to the site PI.

Site PI: [name]/[name]

[name]/[name] are responsible for overall study supervision as well as the following:

Conducting biweekly meetings with all study staff members, troubleshooting recruitment and follow-up challenges, participating in the training of the CHWs, ensuring proper data collection, and general upkeep. The site PI is also responsible for interacting with the protocol director at Stanford, [name]. As this is [name] conception, and she piloted at another site, she will be able to provide [name]/[name] with specific advice and recommendations should challenges arise.

Protocol Director: [name]

[name], PI of the study, is responsible for the overall study including corresponding with the site PI to help troubleshoot any challenges in data collection or follow-up. [name] is also responsible for assisting the sites in implementing the intervention, following study protocols, and responsible for conducting and overseeing data analysis and manuscript publication.

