5.0 STATISTICAL CONSIDERATIONS

5.1 Outcome Measurements

None of the listed outcomes relate to safety.

Primary Outcome Measure

The specific key measurement used to measure the effect of the intervention corresponding to the primary outcome is change in health-related quality of life. The protocol aims primarily to detect a significant (5% significance level) between-group difference from baseline to 4 months (delta

change=4) assuming a within-subject correlation of 0.8 and a standard deviation of the change in score equal to 9.5 based on empirical evidence.

Secondary Outcome Measure

Patient satisfaction and activation will be explored using changes in the Patient Satisfaction with Decision Scale and Patient Activation Measure. Utilization will be measured evaluating comparisons of hospitalizations, emergency department, and referrals to hospice and palliative care. Advanced care planning will be measured by comparing rates of advance directive documentation, Physician Orders for Life-Sustaining Treatment, and goals of care documentation in patients' electronic health record charts. Patient survival will also be compared between groups. Total costs of care will be abstracted from UHH database only to conduct a budget impact analysis and obtain point estimates for refinement of the intervention in anticipation of a larger multi-center trial. A cost-effectiveness analysis is not planned and will not occur until effectiveness has been demonstrated in subsequent studies upon completion of this study.

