3.2 Secondary Outcome(s) – Exploratory Outcomes Only

Health Related Quality of Life is measured by the Functional Assessment of Cancer Therapy-General: a 27-item questionnaire designed to measure four domains of HRQOL in patients with cancer. The scale is on a 5-point Likert-type scale with a score range of 0-108 with higher scores indicating greater HRQoL.

Patient Satisfaction with Decision is measured by the Satisfaction with Decision scale, a six-item scale designed to measure patient satisfaction with healthcare decision. Each item is on a 1-5 scale with higher scores indicating greater satisfaction with decision.

Patient activation is measured by the Patient Activation Measure. Each item rated on 4-point scale (1 strongly disagree to 4 strongly agree, with additional “not applicable” option. Total PAM score = [raw score]/[# items answered excepting non-applicable items] *13 ; can be transformed to a scale with a theoretical range 0–100 based on calibration tables. Raw scores can be converted into activation levels which can also be used as cut-offs:

4. Statistical Analysis Plan

We will present descriptive statistics broken out by intervention group for baseline clinical and demographic variables of interest using continuous (mean, standard deviation, median, interquartile range), and discrete (counts, percentages) where appropriate. We will also tabulate and present for each relevant covariate the percentage of subjects missing a value for that covariate, if applicable.

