4.2. Primary Analysis

All patients will be included in the analysis based on their randomization assignment at time of enrollment using intent to treat. Patient data will be modeled at the participant-level.

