4.2.1. Statistical Modeling

To assess our primary outcome of the effect of the intervention on change in health-related quality of life from baseline to 4-months post-enrollment between groups, we will calculate expected mean differences between groups by Generalized Estimating Equations (GEE) models where the outcome will be modeled as a function of treatment group, categorical time (baseline, 4 months, 12 months) and an interaction term between treatment group and time with an exchangeable correlation clustered within person. Significance will be assessed between groups overtime using a type III F-test on the interaction term. All ratios will be expressed as referent to the control group.

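### The primary exchangeable GEE can bias the 4-month FACT-G effect if health-related loss differs by arm; an unstructured repeated-measures model with tipping-point and death analyses would be safer

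*Combined protocol and SAP*

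**What the plan says.** SAP 3.1 defines the primary outcome as change in FACT-G from baseline to month 4. SAP 4.2.1 models the score at months 0, 4 and 12 with arm, categorical time and an "interaction term between treatment group and time with an exchangeable correlation clustered within person". Baseline FACT-G is part of the outcome vector, not a covariate. No weighting or imputation is stated. The test is also set there: "Significance will be assessed between groups overtime using a type III F-test on the interaction term".

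SAP 4.2 adds: "All patients will be included in the analysis based on their randomization assignment at time of enrollment using intent to treat". The only text on missing data, at the start of SAP section 4, is descriptive and concerns covariates: the "percentage of subjects missing a value for that covariate, if applicable". Nothing covers a missing month-4 FACT-G score or a death before month 4, and no sensitivity analysis for either is named.

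Other sections bear on who may be lost:
- Protocol 3.1 screens "all potential patients with newly diagnosed or recurrent disease no matter the stage or type to determine eligibility".
- Protocol 4.0, for both arms: "If patients feel discomfort while conducting their surveys, they may choose to not complete them".
- Protocol 4.0 gives Arm B at least weekly community health worker contact to month 4; Arm A has usual care coordination.
- Protocol 5.1: "Patient survival will also be compared between groups". SAP 1.1.2 also plans end-of-life outcomes. Deaths are therefore foreseen.

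**The concern.** An unweighted GEE has a general guarantee of consistency only when missingness is completely at random given its covariates, here arm and time. When sicker patients are lost, the model can still use their baseline scores, but only through its working correlation. With an exchangeable structure, that is one correlation and one variance pooled over the 0–4, 0–12 and 4–12 month pairs. If scores 8 or 12 months apart are less correlated than scores 4 months apart, the 12-month data pull the pooled value down, and the month-4 mean is under-corrected. If loss also differs by arm, the error does not cancel.

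The stake is the single confirmatory result. A target of 4 points leaves limited room for an error that the recorded baseline scores could largely remove. Separately, FACT-G is undefined after death, so a reader cannot tell whether the month-4 claim concerns everyone randomized or those alive.

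**Working it through.** **Plan inputs (Protocol 5.1; SAP, Sample Size Considerations).** Target 4 points, SD of change 9.5, within-subject correlation 0.8, 80 per arm.
- Implied SD at a visit: 9.5/√(2 × (1 − 0.8)) = 9.5/√0.4 = 15.02.
- SE of the effect with complete data: 9.5 × √(2/80) = 1.50.
- The plan gives no figure for missing data. Its stated power above 90% is not reproduced with 9.5 as the SD of change: 4/1.502 = 2.663, and Φ(2.663 − 1.960) = 75.9% two-sided. It is exceeded if 9.5 is the SD of a single score (SD of change 9.5 × √0.4 = 6.01, power 98.8%). That is a separate matter, but it means the visit SD could be 9.5 or 15.02, so both are used below.

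**Assumptions, not in the documents.** Loss rates, strength of dependence on baseline, the 0–12 and 4–12 correlations, and any rise in SD.

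**Formula.** Suppose that patients who miss month 4 also miss month 12. In each arm let D be the mean baseline of patients still observed minus the mean baseline of all. Let α be the pooled working correlation and β the true regression slope of month 4 on baseline, β = corr(0,4) × SD₄/SD₀. Solving the estimating equations gives a month-4 mean equal to the observed mean minus α × D. The correct adjustment is β × D. Hence

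bias in the effect = (β − α) × (D_B − D_A).

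It is zero if loss is equal by arm (D_B = D_A) or if α = β.

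**Check against simulation.** Log-odds of loss 1 per SD of baseline, loss 10% in Arm A and 30% in Arm B. The bias of the unadjusted month-4 difference equals β × (D_B − D_A), which gives D_B − D_A.

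| Visit SD; correlations (0–4, 0–12, 4–12) | Unadjusted bias | D_B − D_A | α | (0.80 − α)(D_B − D_A) | Simulated GEE bias |
|---|---|---|---|---|---|
| 15.02; 0.8, 0.5, 0.65 | 1.98 | 1.98/0.8 = 2.48 | 0.62 | 0.18 × 2.48 = 0.45 | +0.45 |
| 9.5; 0.8, 0.5, 0.65 | 1.21 | 1.21/0.8 = 1.51 | 0.62 | 0.18 × 1.51 = 0.27 | +0.24 |
| 9.5; 0.8 throughout | 1.22 | 1.22/0.8 = 1.53 | 0.77 | 0.03 × 1.53 = 0.05 | +0.04 |

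Formula and simulation agree within Monte Carlo error (0.03 to 0.05).

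**Range under baseline-dependent loss, true effect 4, SD₀ = 15.02 unless stated.**

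| Scenario | 10% A / 20% B | 10% A / 30% B |
|---|---|---|
| Steep loss (0.12 log-odds per point = 1.8 per SD); 0.8, 0.5, 0.6 | +0.32 to +0.37 | +0.71 to +0.76 |
| Loss 1 per SD; 0.8, 0.5, 0.6 | +0.27 | +0.44 |
| Loss 1 per SD; 0.8, 0.7, 0.75 | +0.08 | +0.19 |
| Steep loss; SDs 13, 17, 18; 0.8, 0.5, 0.6 | +0.61 to +0.70 | +1.29 to +1.33 |

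Reversing the first row to 20% A / 10% B gives −0.38 to −0.41. Equal loss (15%/15%) gives about 0. With constant SDs and correlation 0.8 throughout, the bias is at most about 0.2. With rising SDs, β = 0.8 × 17/13 = 1.05, which no single correlation can reach; even with every correlation 0.8, the bias was +0.82 at 10%/30%. Two Monte Carlo SEs (2 × 0.045) on +1.33 give the upper figure of about 1.4. A likelihood fit with unstructured covariance stayed within 0.1 in all these cases.

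**Loss that depends on the unseen month-4 score (1 per SD).** At 10%/20% the GEE bias is +0.66 and the unstructured fit +0.49; at 10%/30%, +1.24 and +0.94. About three quarters remains (0.49/0.66 = 0.74; 0.94/1.24 = 0.76). If loss depends on the change itself, baseline adjustment does not help: +1.27 for the GEE and +1.40 for ANCOVA at 10%/30%.

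**The case against.** The strongest reply is that the problem is conditional and may be small. The documents give one correlation, 0.8, and no loss rates. If 0.8 holds for every pair with constant variance, or if loss is equal by arm, the planned GEE is nearly unbiased. With a gentler loss slope and constant SDs the bias is roughly 0.1 to 0.4, against an SE of 1.50. The rising-SD case implies an SD of change of √(13² + 17² − 2 × 0.8 × 13 × 17) = 10.2, not the plan's 9.5. All of this stands and limits the claim to a possibility with a stated range.

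Four stronger readings are tempting and not supported:
- *The GEE is valid only if patients who are lost resemble those who stay.* The results for equal loss and for true exchangeability contradict this.
- *The plan's rules make unequal loss likely, and in the intervention's favour.* The survey opt-out applies to both arms, and staff administer surveys on the same schedule in each. Weekly contact could as well improve retention in Arm B, which biases against the intervention. Protocol 3.2 words its removal rule for one arm ("Any patients or families of patients in the intervention arm who withdraw consent will be removed from the study"), but does not say that collected data are discarded.
- *A mixed model would cure the problem.* It does not when loss follows the unseen score, and it treats death exactly as the GEE does.
- *Deaths shift the primary estimate by a known amount.* If 6% versus 10% died and decedents would have scored 20 points lower, 20 × (0.10 − 0.06) = 0.8 points. That describes a survivors-only mean difference, not the planned change contrast, and the inputs are invented.

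**Conclusion.** The concern holds as a vulnerability of the chosen model, not as a demonstrated bias. The plan relies on an unstated assumption: loss completely at random, or baseline-dependent loss with constant correlation and variance across visits. A mixed-stage cancer population with an optional survey and unequal contact by arm gives reason not to take that for granted. Under the assumed unequal loss, bias with constant SDs is 2.5% to 19% of the target (0.1/4 to 0.75/4), and at most half an SE (0.75/1.50). With rising SDs it could reach 35% (1.4/4). Its sign depends on which arm loses more low-baseline patients. Loss driven by the unseen month-4 score is the larger risk and needs its own sensitivity analysis. The meaning of the result for patients who die before month 4 is a separate gap that no choice of covariance closes. The change is worth making because it is cheap, although its benefit depends on the loss that occurs.

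**What to change.** In SAP 4.2.1:
1. Keep the mean model (arm, categorical time, arm by time) but fit it by REML as a mixed model for repeated measures with unstructured covariance over the three visits. Take the arm difference in change from baseline to month 4 as the primary estimate. Keep the exchangeable GEE as a sensitivity analysis.
2. Add a delta (tipping-point) analysis that shifts the unobserved month-4 scores separately by arm, with the range of shifts fixed before unblinding.
3. State whether the month-4 claim is for all patients or for those alive. Add one supportive analysis in which death before month 4 ranks below every observed change (worst-rank Wilcoxon test).
4. Tabulate missing FACT-G at months 4 and 12 by arm and reason (death, withdrawal, refusal).

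Cost: SAP wording and some programming; no new visits or outcome measures. The covariance has six parameters instead of two, and the fit relies on approximate normality, which is reasonable for a 0–108 score with about 160 patients.

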5.2 Analysis Plan

The Statistical Analysis Plan (SAP) will be prepared prior to the commencement of data analysis. All patients enrolled in the study will be used for the analysis for an intention to treat analysis.

Secondary analyses are for exploratory outcomes only and include differences in satisfaction with decision-making, acute care utilizations and to obtain point estimates on costs of care. Statistical significance of secondary outcomes is for trends only and not represented in this sample size calculation.

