5.3 Sample Size

The primary goal is to improve quality of life. A total of 160 patients are needed to attain significant between-group differences from baseline to 4 months after study enrollment for patients. (See Primary Outcome Measure section above).

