1.1. Study Aims

1.1.1. Aim 1

The primary aim of the LEAPS program is to evaluate whether trained lay health workers who engage newly diagnosed patients with cancer and patients with newly diagnosed relapsed or progressive disease can improve Health-Related Quality of Life (HrQOL) at 4 months post-enrollment compared to baseline more than usual care.

1.1.2. Aim 2

Secondary aims which a priori defined to be exploratory include the effect of the intervention on changes in health-related quality of life from baseline to 12-months post-enrollment as compared to usual care, changes in patient satisfaction with decision-making and patient activation at 4- and 12-months post-enrollment as compared to baseline, change in emergency department and hospital use within 4- and 12-months post-enrollment, advance directive, goals of care documentation, and Physician Orders for Life Sustaining Treatment documentation at 4- and 12-months post-enrollment, and hospice and palliative care use within 4- and 12-months post-enrollment and total costs of care from baseline to death or 12-months follow-up, whichever is first. In addition, we will evaluate emergency department, hospitalization, hospice and palliative care use and total costs of care in the last 30 days of life among those who died.

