3.1. Primary Outcome(s)

Health-related Quality of Life (HRQoL) (change in scores from baseline to 4 months post-enrollment). Health-related quality of life assessed using the 27-item Functional Assessment of Cancer Therapy – General where scores range from 0-108 with higher scores indicating better health-related quality of life.

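### The primary significance test is a joint 2-df group-by-time test over months 4 and 12, so the exploratory 12-month change can decide a primary question that concerns month 4 only

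*Combined protocol and SAP*

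**What the plan says.** The definition of the primary question is consistent. SAP section 3.1 gives the primary outcome as "Health-related Quality of Life (HRQoL) (change in scores from baseline to 4 months post-enrollment", and SAP Aim 1 agrees. Protocol section 5.1 attaches the error rate to that comparison: "The protocol aims primarily to detect a significant (5% significance level) between-group difference from baseline to 4 months". Protocol section 5.3 sizes the trial for it: "A total of 160 patients are needed to attain significant between-group differences from baseline to 4 months after study enrollment".

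The 12-month change has a different status. SAP section 1.1.2 (Aim 2) begins "Secondary aims which a priori defined to be exploratory include the effect of the intervention on changes in health-related quality of life", and the item meant is "changes in health-related quality of life from baseline to 12-months post-enrollment as compared to usual care". Protocol section 5.2 adds, for secondary outcomes in general, "Statistical significance of secondary outcomes is for trends only and not represented in this sample size calculation".

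SAP section 4.2.1 opens by aiming at the 4-month difference and says mean differences between groups will be calculated. The model contains "categorical time (baseline, 4 months, 12 months) and an interaction term between treatment group and time". The only test it names is this: "Significance will be assessed between groups overtime using a type III F-test on the interaction term". Neither the protocol nor the SAP names a 4-month contrast, a gatekeeping step or a closed procedure.

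**The concern.** The endpoint and the test do not match. The 4-month change is one of two components of the tested hypothesis and is not isolated. The other component is an outcome that the SAP itself calls exploratory.

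If the rule is followed as written, three things can happen.

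- The primary result can be significant because of month 12 alone, with nothing at month 4. The 5% level in protocol section 5.1 is then not the error rate of the 4-month claim.
- The direction of the month-12 difference does not matter: harm at month 12 triggers the test as readily as benefit.
- The primary p-value can contradict the estimated 4-month difference that the same section promises.

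If the analysts notice this later and switch to a 4-month contrast, that choice will be unplanned.

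**Working it through.** **Inputs from the documents.** 80 per arm, target difference 4 points, SD of change 9.5 and within-subject correlation 0.8 (SAP, Sample Size Considerations); 5% level (protocol 5.1); three categorical times and exchangeable correlation (SAP 4.2.1).

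**Assumptions.** Two-sided testing, equal variances over time, exchangeable as the true correlation, and complete data unless stated. The documents give no expected 12-month effect, so all month-12 differences are illustrative.

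**The plan's own figure.** For a 4-point difference the standard error is 9.5 × √(2/80) = 1.502, and 4/1.502 = 2.66. Two-sided power on t(158) is 75.4% (75.9% by the normal approximation), not the stated figure of more than 90%. Reading 9.5 as the SD of the score gives an SD of change of 9.5 × √(2 × 0.2) = 6.01 and power of about 99%, but that is not what the text says. This is a separate matter, and the present point does not depend on it.

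**Degrees of freedom.** (2 − 1) × (3 − 1) = 2.

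**Covariance of the two changes.** Under exchangeable correlation ρ and score variance σ², each change has variance 2σ²(1 − ρ) and their covariance is σ²(1 − ρ). Their correlation is 0.5 whatever ρ is. With SD 9.5, the variance is 90.25 and the covariance 45.125.

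**Noncentrality.** Let d4 and d12 be the true between-arm differences in change at months 4 and 12. Then

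λ = (80/2) × (d4² − d4·d12 + d12²) / (0.75 × 90.25) = 40 × (d4² − d4·d12 + d12²) / 67.69,

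referred to F(2, 158) at 5%. For example, (0, 2) gives 40 × 4/67.69 = 2.36, and (4, 2) gives 40 × 12/67.69 = 7.09.

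| d4, d12 | λ | Joint 2-df test rejects | 4-month contrast rejects |
|---|---|---|---|
| 0, 1 | 0.59 | 9.6% | 5% |
| 0, 2 | 2.36 | 25.6% | 5% |
| 0, 4 or 0, −4 | 9.46 | 78.4% | 5% |
| 4, 0 | 9.46 | 78.4% | 75.4% |
| 4, 1 | 7.68 | 69.0% | 75.4% |
| 4, 2 | 7.09 | 65.3% | 75.4% |
| 4, 3 | 7.68 | 69.0% | 75.4% |
| 4, 4 | 9.46 | 78.4% | 75.4% |

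Simulation with robust variance (20,000 trials per case) agrees: 9.9%, 26.1% and 78.4% for the first three rows, and 5.2% when there is no effect at either time.

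**Disagreement when the 4-month effect is truly 4 points.** In the same simulations the verdicts differ in 13.8%, 12.8%, 12.8%, 12.9% and 14.0% of trials for d12 = 0, 1, 2, 3 and 4. At (4, 2), 11.3% are significant by the contrast only and 1.5% by the joint test only.

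**Missing data.** Assume that 20% or 40% lack month 12 and that one third of those also lack month 4. The month-12-only rejection rates become 8.7% or 7.8% (1 point), 21.3% or 17.0% (2 points), and 68.6% or 55.7% (4 points).

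**Other readings.**

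- With SD of change 6.01, a 2-point month-12-only difference is significant in about 57% of trials. Disagreement for a true 4-point month-4 effect, checked at d12 = 0, 2 and 4, falls to about 1% to 2%.
- If correlation decays with time (assumed 0.8, 0.8 and 0.64), the month-12-only rates at SD 9.5 are 8.5%, 20% and 66%.

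**The case against.** The strongest reply is that the intent is plain. Section 4.2.1 opens with the 4-month change, and protocol 5.1 attaches the 5% level to it, so the test sentence could be read as unfinished. That shows what was meant, but protocol 5.1 gives a level without a test, and the one test named is the joint one. The public SAP also skips section numbers (4.2.1 is followed by 4.2.2.1). That limits any claim of absence to the visible text, but it does not show that a contrast exists.

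It is fair to say that the joint test holds 5% when there is no effect at either time. An effect at month 12 with none at month 4 is also not what the design anticipates, since minimum contact drops from weekly to monthly after month 4. The 4-point case in particular is extreme. These points bear on how often the problem would bite, not on whether the test answers the primary question.

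Two narrower points also stand. Protocol 5.2 does not name 12-month quality of life, so its exploratory status rests on SAP Aim 2. And the joint test is not uniformly weaker: it is sometimes more powerful than the contrast, so the complaint cannot be one of lost power.

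**Conclusion.** The concern holds, and the rule should be changed before analysis. As written, it tests a hypothesis other than the declared primary one, and a rejection cannot be attributed to month 4. The 2 degrees of freedom and the mismatch follow from the text alone and need no assumption about variance.

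The size does rest on assumptions. Across the scenarios worked at SD 9.5, with no 4-month effect, the chance of a significant primary result runs from about 8% to 10% for a 1-point month-12 difference and from 17% to 26% for 2 points. It runs from 56% to 78% for 4 points. A 4-month contrast would stay at 5%. If the SD of change is nearer 6, these rates are higher.

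**What to change.** Replace the significance sentence in SAP section 4.2.1 with wording such as: *The primary test is the single-degree-of-freedom treatment-by-month-4 contrast (difference between arms in change from baseline to 4 months) from this model, two-sided 5%, reported with its 95% confidence interval.* Label the treatment-by-month-12 contrast and the 2-df interaction test as exploratory.

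The change costs one sentence and uses the same model and data. Under exchangeable correlation and complete data, for a true 4-point effect at month 4, power is 3 points lower than the joint test (75% against 78%) if the month-12 effect is 0 or 4 points. It is 6 to 10 points higher if the month-12 effect is 1 to 3 points. Under the decaying correlation assumed above, the cost could reach about 15 points if the effect has gone by month 12 (75% against 90%). If it persists in full, the contrast gains about 10 points (75% against 66%). The change does not repair the separate gap between the stated power and the 75% computed here.
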